Control Status: Not Well Controlled or Well Control	
“Not Well Controlled” if patient has any one of the following events
 
 • Prescription for OCS • Asthma-related ER • Asthma-related hospitalizations 
“Well controlled” if patient has none of the above events
 
(Ref: Stempel JACI 2005)
	PSM
ICS history	Defined by use of ICS monotherapy prior to index date	PSM
ICS history duration	Days on ICS monotherapy prior to index date	PSM
ICS dose level	Daily dose of ICS classified as low dose ICS, medium dose ICS, and high dose ICS	PSM
Season	Season of cohort entry (Summer, Spring, Fall, Winter)	PSM
Index year	Year of the index date	PSM
All-cause resource use	All-cause hospitalizations, ER visits, outpatient visits	PSM
Other asthma medications	Leukotriene modifiers	PSM
Medication history	Polypharmacy calculated based on number of unique medications	PSM
Insurance type	Identified using payer type data field	PSM
Hypertension	Identified using appropriate ICD codes. Coded as binary (yes/no) variables	PSM
Allergic rhinitis	Identified using appropriate ICD codes. Coded as binary (yes/no) variables	PSM
Sinusitis	Identified using appropriate ICD codes. Coded as binary (yes/no) variables	PSM
Obstructive sleep apnea	Identified using appropriate ICD codes. Coded as binary (yes/no) variables	PSM
Gastro-esophageal reflux disease	Identified using appropriate ICD codes. Coded as binary (yes/no) variables	PSM
Obesity	Identified using appropriate ICD codes. Coded as binary (yes/no) variables	PSM
Cardiovascular disease	Identified using appropriate ICD codes. Coded as binary (yes/no) variables	PSM
Diabetes	Identified using appropriate ICD codes. Coded as binary (yes/no) variables	PSM

Proprietary confidential information © 2021 Boehringer Ingelheim International GmbH or one or more of its affiliated companies

Table 1: Baseline Parameters and Variable Definitions (cont)

Variable Name and Type	Description and Definition	Covariate Adjustment Method
Renal failure	Identified using appropriate ICD codes. Coded as binary (yes/no) variables	PSM
Arthritis	Identified using appropriate ICD codes. Coded as binary (yes/no) variables	PSM
Depression	Identified using appropriate ICD codes. Coded as binary (yes/no) variables	PSM
Osteoporosis	Identified using appropriate ICD codes. Coded as binary (yes/no) variables	PSM
Cancer (excluding basal cell carcinoma)	Identified using appropriate ICD codes. Coded as binary (yes/no) variables	PSM

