Pneumonia	Identified using appropriate ICD codes. Coded as binary (yes/no) variables	PSM
Acute bronchitis	Identified using appropriate ICD codes. Coded as binary (yes/no) variables	PSM
Dyspnea	Identified using appropriate ICD codes. Coded as binary (yes/no) variables	PSM
Alcohol dependence	Identified using appropriate ICD codes. Coded as binary (yes/no) variables	PSM
Smoking dependence	Identified using appropriate ICD codes. Coded as binary (yes/no) variables	PSM

Using propensity score matching (PSM) technique, we will develop matched cohorts of patients between the ICS+Tio and ICS/LABA groups. We will conduct 1:2 matching using nearest neighbor matching approach. Upon completion of matching, we will assess whether the cohorts are balanced by examining the statistically significant differences at $p < 0.05$. We will also assess balance by calculating standardized mean differences (SMD). An SMD < 0.1 will be considered balanced. Follow-up time will be calculated between index date and 'Censor date' which will be defined as the date of either one of the following events: 1. Date of first exacerbation, 2. Date of medication switch, 3. Discontinuation of medication (defined as date of prescription claim plus days' supply, plus 50% additional days), 4. Enrollment end date, or 5. Last date available in the dataset/End of study period. In this "new user", study design, primary analysis will be an "as-treated" analysis. In order to attribute events and outcomes to patients during the time that they are exposed to treatment (based on days-supply of prescription claims + a buffer window) as well as account for differences in inter-group adherence levels, we will use a time-varying covariate approach to classify drug exposure time for each comparator drug during follow up. This approach has been chosen to minimize bias based on potentially large differences in medication adherence rates, by only attributing outcomes to the time in which patients have medication in their possession based on days' supply as described below. For each individual study drug, we will identify and define medication exposure and non-exposure windows during the follow-up time for each medication using the date of prescription filled plus the days' supply listed on the prescription claim plus 50% additional days (to account for residual doses in canister, poor real-world adherence and latency of drug effects). For example, exposure start and stop dates

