Proprietary confidential information © 2021 Boehringer Ingelheim International GmbH or one or more of its affiliated companies for a patient with a prescription claim with 30 days supply on January 1st will be January 1st and February 15th respectively (30 days' supply +15 days). We will run sensitivity analyses on the exposure window using 0% and 100% additional days. These time varying exposure covariates will be included in the Cox PH regression.

If statistical differences are found after PSM, then the study team will make a determination to either include them as covariates in the regression analysis (Cox PH), or develop interaction terms to match on, or discontinue the study. In the event of study discontinuation, partial results (all analysis leading up to and including PSM) will be provided in a final report.

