9.3.2 Endpoints

9.3.2.1 Primary endpoints

[figure not shown]
The primary endpoint measure is time to first severe exacerbation. Severe exacerbations will be defined as:

- A hospitalization with a primary diagnosis of asthma or
- An ER visit with a primary diagnosis of asthma

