9.3.2.2 Secondary endpoints

Secondary endpoints will include:

- Time to first moderate-or-severe exacerbation
 - Any systemic corticosteroid use or
 - A hospitalization with a primary diagnosis of asthma or
 - An ER visit with a primary diagnosis of asthma
- Proportion of patients with exacerbation
- Rate of exacerbation at 6 months and one year
- Proportions of patients with Health care resource utilization (HCRU). HCRU is defined as hospitalizations, emergency room (ER) visits, and outpatient visits during follow-up, all-cause and asthma related.
- Mean monthly HCRU (including frequency of hospitalizations, ER visits, OP visits)
- Proportion of patients with use of rescue medications (defined as patients with one or more SABA claims during the follow-up period)

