9.3.3 Covariates

The covariates included in the PSM will be

- Gender
- Age group
- Region
- ICS dose level
- Control level
- Rescue medication use
- Comorbidities included in the Charlson Comorbidity Index
- ICS history (yes/no)
- ICS history duration
- Season of index date
- Index year
- Baseline all-cause resource use (presence vs. absences of hospitalizations, or ER visits, or outpatient visits)
- Baseline other asthma medications (use vs. no use)

Proprietary confidential information © 2021 Boehringer Ingelheim International GmbH or one or more of its affiliated companies

- Baseline overall medication history (polypharmacy defined as number of unique medications)
- Insurance type
- Hypertension
- Gastroesophageal reflux disease
- Allergic Rhinitis
- Obesity
- Sinusitis
- Obstructive sleep apnea
- Cardiovascular disease
- Diabetes
- Renal failure
- Arthritis
- Osteoporosis
- Depression
- Cancer (excluding basal cell carcinoma)
- Baseline pneumonia diagnosis
- Baseline acute bronchitis diagnosis
- Diagnosis of dyspnea during baseline identified using ICD 9 786.0x and ICD 10 R06.0x
- Diagnosis of alcohol dependence during baseline identified using ICD 9 303.xx, 305.0x and ICD 10 F10.xx
- Smoking dependence during baseline identified using ICD 9 305.1 and ICD 10 F17.xx

In addition to the key independent variable of interest (ICS+TIO vs ICS/LABA group), we will include time varying medication exposure as a covariate in the regression.

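### Prior severe exacerbation, the baseline counterpart of the primary endpoint, enters the propensity score only in pooled form, so an imbalance in it could go unmatched and untested

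*Combined protocol and SAP*

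**What the plan says.** Section 9.3.2.1 defines the primary event as an asthma hospitalization or "An ER visit with a primary diagnosis of asthma". The secondary moderate-or-severe endpoint in 9.3.2.2 adds "Any systemic corticosteroid use".

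Table 1 in 9.1 defines control status as two levels. A patient is not well controlled "if patient has any one of the following events": an OCS prescription, an asthma-related ER visit or an asthma-related hospitalization. Resource use is a separate row, "All-cause hospitalizations, ER visits, outpatient visits", with no coding rule. Section 9.3.3 and the abstract describe it as "Baseline all-cause resource use (presence vs. absences of hospitalizations, or ER visits, or outpatient visits".

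On balance, 9.1 says "we will assess whether the cohorts are balanced by examining the statistically significant differences" at p < 0.05, and "An SMD < 0.1 will be considered balanced". It continues: "If statistical differences are found after PSM, then the study team will make a determination" to add the variables to the Cox model, match on interaction terms, or discontinue the study. Apart from that fallback, the regression contains only the treatment group and time-varying exposure (9.3.3).

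**The concern.** A patient with one OCS prescription and a patient with several asthma admissions get the same value of the control flag. The flag is therefore roughly the baseline version of the secondary endpoint, not of the primary one. The other route, all-cause use, mixes asthma admissions and ER visits with those for any other cause. Nothing in Table 1, 9.3.3 or the abstract list separates out prior asthma ER visits or hospitalizations.

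A history of the outcome event is an obvious candidate confounder for time to the next such event. Matching can equalise the share of not-well-controlled patients while leaving a different mix of OCS-only and prior-severe patients inside that share. The balance checks and the fallback rule operate on listed covariates, so they would not see the difference, and the primary hazard ratio could absorb it.

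**Working it through.** The plan states no figure on this point, so there is nothing to reproduce. The calculation below only illustrates scale. **Every input is an assumption; the documents supply none of them.**

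**Inputs**
- p = 0.40, share not well controlled, equal in both arms (the flag is perfectly balanced).
- h = 1.5, hazard of OCS-only patients relative to well-controlled patients.
- k = 2, 3 or 4, hazard of prior-severe patients relative to OCS-only patients.
- s, share of the cohort with a prior severe event, higher in the Tio arm. Reversing the imbalance reverses the bias.

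**Formulas**
- Average hazard = (1 − p) + (p − s)h + s·h·k. The ratio between arms, with no treatment effect, approximates the spurious hazard ratio.
- Hidden SMD = (s₁ − s₂) / √{[s₁(1 − s₁) + s₂(1 − s₂)]/2}.

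**Reading B: three separate all-cause flags, each balanced.** Take 20% of each arm with hospital or ER use. An asthma share of 35% versus 25% gives s = 0.07 versus 0.05; 30% versus 25% gives 0.06 versus 0.05.

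**Reading A: one composite that includes outpatient visits, which constrains almost nothing.** Prior severe events in 25% versus 15% of the not-well-controlled give s = 0.10 versus 0.06; 20% versus 15% gives 0.08 versus 0.06.

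| Reading | s (Tio vs LABA) | k = 2 | k = 3 | k = 4 | Hidden SMD |
|---|---|---|---|---|---|
| B | 0.07 vs 0.05 | 1.305/1.275 = 1.024 | 1.410/1.350 = 1.044 | 1.515/1.425 = 1.063 | 0.084 |
| B | 0.06 vs 0.05 | 1.290/1.275 = 1.012 | 1.380/1.350 = 1.022 | 1.470/1.425 = 1.032 | 0.044 |
| A | 0.10 vs 0.06 | 1.350/1.290 = 1.047 | 1.500/1.380 = 1.087 | 1.650/1.470 = 1.122 | 0.148 |
| A | 0.08 vs 0.06 | 1.320/1.290 = 1.023 | 1.440/1.380 = 1.043 | 1.560/1.470 = 1.061 | 0.078 |

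**Allowing for non-asthma hospital and ER users.** Under Reading B total all-cause use is equal, so the arm with fewer asthma users has more non-asthma users. Give the latter a multiplier m and write u = 0.20 for all-cause hospital or ER use. The hazard becomes [(1 − p) + (p − s)h]·[1 + (m − 1)(u − s)/(1 − s)] + s·h·k. For 0.07 versus 0.05 and k = 2, 3, 4:
- m = 1.5: 1.013, 1.033, 1.051.
- m = 2: 1.004, 1.023, 1.041.

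**Wider inputs.** With p 0.2–0.6, h 1–2, k 2–4, the same 5- or 10-point gaps, and under Reading B all-cause use of 15–25% with m = 1, Reading B spans 1.01–1.10 and Reading A 1.01–1.17.

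**Would the p < 0.05 check react if the components were listed?** For 1:2 matching and an unpaired two-proportion z test, the expected z reaches 1.96 at N(Tio) = 1.96²·p̄(1 − p̄)·1.5/d², where d is the difference and p̄ the pooled share.
- 7% vs 5%: p̄ = 0.0567, d = 0.02, N ≈ 770, which is 4.3% of the 17,882 Tio patients in 9.5. An expected z of 1.96 is only about 50% power; replacing 1.96 by 1.96 + 0.84 gives about 1,570 for 80%.
- 6% vs 5%: N ≈ 2,909 for about 50% power, 16.3% of 17,882.

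**The case against.** **The history is pooled, not omitted.** Asthma-related ER visits and hospitalizations are two of the three triggers of the flag, and all-cause use is matched as well. With three separate flags, a patient without hospital or ER use cannot have had a prior severe event, so hidden imbalance is confined to flagged patients who also used a hospital or ER. Rescue medication, ICS dose, leukotriene modifiers, polypharmacy, acute bronchitis, pneumonia and dyspnea are further proxies. This stands. It limits the size of the problem but does not remove it, because none of these variables records a prior severe exacerbation.

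**The larger figures need the weaker reading.** A reader might infer a bias of 10% or more. In the base case that requires all-cause use to be one composite that includes outpatient visits. Such a variable would probably be near-constant in a cohort required to have two asthma diagnoses. Table 1 names three types of use and 9.3.2.2 reports them as separate types, so three flags is the more natural reading. This stands too, although the wording in 9.3.3 leaves the composite open.

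**The control definition is referenced.** Table 1 cites a published claims analysis for it. A citation for classifying control does not show that the flag is sufficient adjustment for a narrower endpoint.

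**Listing the components would not by itself solve it.** A reader might infer that the significance check would then catch the imbalance. By the arithmetic above it has about 50% power at 770 matched Tio patients, and the final matched number is unknown. The Reading B base-case SMDs also lie below the plan's own 0.1 limit. The main gain comes from matching on the components.

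**Conclusion.** The point holds as a worthwhile and inexpensive improvement. Followed exactly, the plan leaves the asthma-specific history of the primary event unmatched in its own right and untested for balance, although the claims needed to separate it are already required to build the flag.

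On the three-flag reading the illustrative bias is about 1.01–1.06 with a hidden SMD of 0.04–0.08. For 7% versus 5% it is about 1.00–1.05 if non-asthma hospital and ER users have 1.5–2 times the risk, and balance on correlated covariates would reduce it further. Only on the composite reading does the base case reach about 1.02–1.12. All of this rests on assumed prevalences and hazards. The documents do not show that an imbalance exists or which arm it would favour, so they do not support a claim that the primary hazard ratio is biased, only that it could be without the plan noticing.

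Nor do the documents support reading the post-matching rule in 9.1 as a commitment to adjust. It leaves the team a choice between adjusting, matching on interaction terms and discontinuing.

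**What to change.** In Table 1, 9.3.3 and the abstract list:

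- Keep the control flag, which also retains asthma-related events coded in a secondary position.
- Add to the propensity score separate 6-month baseline covariates for asthma hospitalization and asthma ER visit (both by primary diagnosis, matching the endpoint) and for OCS prescriptions. Code them 0/1/2+ where numbers allow, otherwise yes/no.
- State that all-cause hospitalization, ER and outpatient use are three separate variables.
- Report the SMD of each component before and after matching.
- Add a new pre-specified rule that any of these components still imbalanced after matching enters the Cox model. This would be new, because the present text leaves the response to the team.

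The cost is a few overlapping score terms and possibly slightly fewer matches. Section 9.5 gives 921,804/17,882, or about 51 ICS/LABA patients per Tio patient. That is before the remaining criteria, including concurrent ICS monotherapy, so the final ratio is unknown. The change should be made before matching is run.

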9. RESEARCH METHODS

9.1 STUDY DESIGN

1. Patients with least two asthma diagnosis (ICD 9 CM: 493.xx or ICD 10: J45-J45.999) will be included.
2. Patients will be required to be concurrently on ICS+Tiotropium (specifically Tiotropium Respimat® 1.25 mcg) or ICS/LABA.
3. Patients with least two diagnosis of COPD at any time during the study period will be excluded.
4. Patients less than 12 years of age will be excluded.
5. Patients will be required to have enrollment for at least 6 months prior to ICS+Tio or ICS/LABA use.
6. Patients on biologics within 6 months prior to ICS+Tio or ICS/LABA use will be excluded.
7. Patients with prior Tio or ICS/LABA use during the 6-month baseline period will be excluded.
8. Patients with urinary bladder obstruction, urinary retention, and glaucoma will be excluded.
9. After the PSM process, unmatched patients will be excluded.

Patients will be classified into two groups based on the exposure on the index date: 1. ICS+Tio; and 2: ICS/LABA. The date of concurrent medication initiation will be defined as the index date based on the date of the first prescription claim defining their add-on medication. We will record various baseline measures, including demographics such as gender, age, and region, comorbidity level defined using Charlson Comorbidity Index (CCI), other specific comorbidities not included in the CCI ([Table 1](#)), inhaled medication use, and control level as defined in Table 1. Additionally, we will classify patients based on their daily ICS dose levels as 'low dose ICS', 'medium dose ICS', and 'high dose ICS'. The dose levels will be assigned per GINA 2020 criteria (Global Initiative for Asthma. Global Strategy for Asthma Management and Prevention 2020). Medications that are available with only two dose level indications will be tagged as 'low' for the lower of the two dose levels, and 'high' for the highest dose level.

Proprietary confidential information © 2021 Boehringer Ingelheim International GmbH or one or more of its affiliated companies

Table 1: Baseline Parameters and Variable Definitions

Variable Name and Type	Description and Definition	Covariate Adjustment Method
Demographics	Age (5-year increments), Gender,	PSM
Region	Region (Northeast, Midwest, South, West)	PSM
CCI	Charlson Comorbidity Index score	PSM
Inhaled medication use	Identified using unique claims during the baseline period	PSM

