9.5 STUDY SIZE

There are 25,291 patients with a prescription claim for tiotropium (1.25mcg, October 2015-May 2020) identified for analysis and 1,125,657 patients with ICS/LABA prescription claims (July 2014-May 2020). After excluding patients with COPD there are 17,882 patients in the Tio group and 921,804 patients in the ICS/LABA group. Further inclusion-exclusion criteria as well as restricting the Tio group to those with concurrent ICS monotherapy, will be applied to arrive at the final sample.

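### Prior ICS monotherapy is matched only as yes/no and total days, with no recency condition, so lapsed ICS/LABA starters can be paired unseen with ICS+Tio patients stepping up from current ICS

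*Combined protocol and SAP*

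**What the plan says.** In section 9.1, Table 1 has two rows on earlier ICS treatment, both assigned to propensity score matching. ICS history is "Defined by use of ICS monotherapy prior to index date". ICS history duration is "Days on ICS monotherapy prior to index date". Section 9.3.3 repeats both items without adding a definition.

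The table is headed "Table 1: Baseline Parameters and Variable Definitions". One of its rows, inhaled medication use, names its window: "Identified using unique claims during the baseline period". The length of that period appears in the eligibility list: "Patients with prior Tio or ICS/LABA use during the 6-month baseline period will be excluded". Enrolment has a minimum and no maximum: "Patients will be required to have enrollment for at least 6 months prior to ICS+Tio or ICS/LABA use".

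The arms differ in what they require. Section 9.5 speaks of "restricting the Tio group to those with concurrent ICS monotherapy". Nothing equivalent applies to ICS/LABA, where the combination supplies the ICS. Index is the date on which the add-on drug is initially dispensed. Matching is 1:2 nearest neighbour. Balance is judged by p < 0.05 and by a standardized mean difference (SMD) below 0.1.

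**The concern.** Adding a second drug while ICS is in use and restarting treatment after a gap are different clinical situations, and their exacerbation risks may differ. If the mix of the two differs between arms, the Tio-versus-LABA hazard ratio carries part of that difference.

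The matching variables cannot separate the two situations. They record that ICS monotherapy was used and for how many days, but not when it ended. The remedies in section 9.1 for residual imbalance (covariate adjustment, interaction terms, stopping the study) apply when differences are found after matching. These two variables would give no such signal, because they can balance while current use at index does not.

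**Working it through.** The plan gives no figure to reproduce here. The check is on the text, with date arithmetic and one illustration.

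**1. Does any rule or covariate capture ICS use at index?**
- ICS history and ICS history duration: no end date and no maximum gap to index.
- Inhaled medication use: confined to the baseline period, but not specific to ICS, and absent from the matching lists in section 9.3.3 and the abstract.
- Eligibility: concurrent ICS monotherapy is required for ICS+Tio only.

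So no item does this. Take one patient with 90 ICS days ending at index and another with 90 days ending well before it. Both score yes and 90.

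**2. How far back can the history reach?** Inputs: data from 2014 to 2020 (section 9.4) and the claim windows in section 9.5. Assumptions: data start on 1 January 2014 and the patient is enrolled throughout.
- Index 1 July 2014 (first ICS/LABA month): 181 days
- Index 1 October 2015 (first tiotropium month): 638 days
- Index 31 May 2020: 2,342 days, about 6.4 years

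This is the reach if the rows are read literally. Matching on index year limits calendar differences, but not differences in individual enrolment length, which is not a covariate.

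**3. Does a 6-month window solve it?** Assume the heading does imply the baseline, taken as 183 days. Section 9.1 extends each fill by 50%, so a 30-day fill covers 45 days. A single fill on the first day of the window leaves a gap before index of:
- 50% extension: 183 − 45 = 138 days
- 0% extension (planned sensitivity analysis): 183 − 30 = 153 days
- 100% extension (planned sensitivity analysis): 183 − 60 = 123 days

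The window question would be settled. The recency question would not.

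**4. What could it do to the hazard ratio?** This is illustration only, since none of the inputs is in the documents. Let c1 and c0 be the shares of current users among patients with ICS history in the ICS+Tio and ICS/LABA arms, and h the risk of current relative to lapsed users. Approximately,

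factor on the hazard ratio = [(1 − c1) + c1·h] / [(1 − c0) + c0·h]

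| c1 | c0 | h = 0.7 | h = 1.5 |
|---|---|---|---|
| 0.9 | 0.5 | 0.73/0.85 = 0.859 | 1.45/1.25 = 1.160 |
| 0.9 | 0.7 | 0.73/0.79 = 0.924 | 1.45/1.35 = 1.074 |
| equal to c0 | equal to c1 | 1.00 | 1.00 |

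These factors hold only among patients with ICS history. Suppose half of each arm has such history and the rest carry the lapsed-level risk (also assumed). The first row then shrinks to (0.5 + 0.5×0.73)/(0.5 + 0.5×0.85) = 0.94 and (0.5 + 0.5×1.45)/(0.5 + 0.5×1.25) = 1.09.

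**The case against.** **The heading may set the window.** Only one row of Table 1 names the baseline period; control status, resource use and the comorbidity rows are undated too. In section 9.3.3, control level, rescue medication use and ICS dose level also lack the baseline label. It is reasonable to read the heading as applying the 6 months to every row. This stands. A reader might infer that the plan counts ICS fills up to six years old, but the documents permit that reading without establishing it. The objection does not reach recency within the window.

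**The ICS+Tio arm may also contain restarters.** A reader might infer that this arm consists mostly of current ICS users adding a drug. The documents do not say so: concurrent ICS monotherapy is required, but ICS before index is not, so ICS and tiotropium could start together. Lapsed users can occur in both arms, and unequal shares are a possibility that has not been shown. This stands.

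**Other covariates may help.** Inhaled medication use is marked for matching in Table 1 and may partly separate recent from lapsed users. Control status, rescue use, leukotriene modifiers, resource use and ICS dose level may absorb some of the risk difference. This stands in part: none of them measures ICS monotherapy at index.

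**The size is unknown.** A reader might take 0.86 to 1.16 as the error in the study's hazard ratio. That range comes from assumed inputs, applies only to patients with ICS history, and lies on both sides of 1. This stands.

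**Conclusion.** The gap is real, and it is one of measurement. The matching variables describe earlier ICS monotherapy by presence and amount, with no recency condition and no explicit look-back. Because the concurrency requirement applies to one arm only, current and lapsed users can be matched on identical values, and the planned balance checks on those two variables would not reveal it.

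The documents do not show that such pairs will be common or that the hazard ratio is wrong by any given amount. Size and direction are undetermined, and with equal current-user shares in the two arms there is no bias from this source. The conclusion does not depend on how the window is read: under a 183-day baseline the gap can still be 138 days for a single 30-day fill. The change should be made before matching is run, because it improves control of a plausible confounder of the primary comparison at little cost.

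**What to change.** In Table 1 and section 9.3.3:

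1. Add to the propensity score a three-level ICS-monotherapy status just before index. *Current*: a fill dated before index whose supply, extended by the plan's 50%, reaches the index date. *Lapsed*: ICS monotherapy in the 6-month baseline, but not current. *None*: no ICS monotherapy in the baseline. Requiring the fill to precede index keeps an ICS first dispensed together with tiotropium from counting as current use.
2. State that ICS history duration counts days within the fixed 6-month baseline.
3. Report the distribution of the new status by arm, before and after matching, with its SMD.

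Exact matching on status is optional. The counts in section 9.5 give 921,804/17,882, or about 52 ICS/LABA patients per tiotropium patient, but they precede the remaining exclusions and the ICS-monotherapy restriction. The decision should wait until the final comparator pool is known.

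The cost is a small derivation from pharmacy claims already being extracted, and possibly some loss of matches.
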